5.3 Selection and Screening of Subjects

The study population for this clinical trial will be comprised of patients who have been diagnosed with intracranial aneurysms. In addition, these patients must satisfy all study inclusion and exclusion criteria. The trial will prospectively enroll and randomize up to 600 Subjects in a 1:1 ratio within only one stratification factor: participating site. The investigator or an approved member of the research team will review the patient's medical history for study eligibility and will fully inform any potential candidates about the purpose of the study. The difference between both types of coiling systems will be described and the potential risks and benefits will be explained in detail to each study candidate. Patients who voluntarily agree to participate in the trial will be asked to sign and date the Informed Consent Form (ICF). In the event a patient is unfit to provide signed informed consent (e.g. drowsy/confused), his/her Legally Authorized Representative (LAR) can sign the consent form. Once enrolled into the study, each participant will be assigned a study number. Patient names or identifiers will not be used on any study related documents. An electronic case report form (eCRF) will be completed at the end of each procedure and after each study related follow-up. Only the Principal Investigator of the study ([name]) and authorized members of the Sponsor including study monitors and auditors will have full access to the eCRF. Information from the eCRF will be entered into a secure, password protected study database. The Funder and its employees will have read-only access to collected eCRF study data, as provided by Northwestern, solely for review and adjudication of information related to any AE, SAE, ADE and UADE (as such terms are defined below) for legal and compliance purposes.

If a subject becomes pregnant while participating in this study, any angiographic follow-up will be done using non-contrast MRA as per standard of care.

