9.1 Sample Size Estimation

For univariate associations, using a two-sided two-sample test of proportions (Chi-square test), Table 5 shows the effect sizes one would be able to detect for given baseline rates (assuming 1:1 randomization and 5% type I error rate) at 80% power.

Using multiple logistic regression to predict recurrence (baseline rate in Platinum group of 33%), the sample of 600 patients would provide 80% power to detect an odds ratio between 0.60 and 0.47, depending on the r-squared of the other covariates to coils (between 0-0.2; note r-squared of 0 corresponds to hydrogel rate of 22.8% as in the univariate analysis). Likewise, for complete occlusion (baseline rate of .556), a sample of 600 provides 80% power to detect odds ratios between 1.60-1.70, depending on the r-squared of the other covariates to coils (between 0-0.2; note r-squared of 0 corresponds to hydrogel rate of .678 as above). Similarly, for recanalization, one would have 80% power to detect odds ratios between 0.613-0.577 (n=600).

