9.2 Statistical Analysis Plan

9.2.1 Primary endpoints:

Chi-square tests (simple logistic regression) will be used to determine if rates of recurrence differ by coil type. Additionally, multiple logistic regression models will be used to examine those rates while adjusting for various covariates, including, but not limited to: site, age, gender, aneurysm size, neck size, packing density and rupture status. Models will be fit to examine potential interactions between covariates and randomization group in predicting outcomes; and final models will be fit depending on statistical and clinical significance of the covariates to the outcome as well as any change in the relationship between the randomization group and outcome. Analyses will be presented both as univariate and adjusted Odds Ratios and corresponding [Wald] 95% Confidence intervals.

While the study has been designed to minimize any missing data due to this being a longitudinal study, the potential for missing data or loss to follow-up is present. Patterns of missing data and dropout will be examined to determine if complete case analysis or available data analyses are appropriate or if imputation methods will need to be incorporated. Should a complete case analysis be appropriate, PROC LOGISTIC will be used to analyze these binary outcomes; otherwise PROC GLIMMIX will be used for an available data analysis. If imputation methods are called for, PROC MI and PROC MIANALYSE will be used and results presented. All analyses will be run at a type I error rate of 5% using SASv9.2, Cary, NC.

9.2.2 Secondary endpoints:

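### The adjusted recurrence model can be chosen on its own treatment effect and may include packing density, so its 5% error rate is not assured

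*Combined protocol and SAP*

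**What the plan says.** Section 9.2.1 first compares recurrence by coil type with a chi-square test, equivalently simple logistic regression. In addition it fits multiple logistic models. The candidates named are site, age, gender, aneurysm size, neck size, packing density and rupture status, and the list is expressly left open. Covariate-by-arm interactions are examined. Then "final models will be fit depending on statistical and clinical significance of the covariates to the outcome", together with "any change in the relationship between the randomization group and outcome".

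Univariate and adjusted odds ratios are both reported with Wald 95% intervals, and "All analyses will be run at a type I error rate of 5% using SASv9.2, Cary, NC". Neither odds ratio is named as the one that decides. Section 9.1 gives power for both the two-proportion test and multiple logistic regression. Section 9.2.2 handles the binary secondary outcomes in the same way, so the rule reaches those too.

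Two facts elsewhere bear on the candidate list. Section 5.3 randomises "within only one stratification factor: participating site". Packing density is a secondary outcome in section 4.3, and the hypothesis in section 4.1 is that it is higher with hydrogel.

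**The concern.** Choosing covariates by their effect on the exposure estimate is a device for controlling confounding in observational data. In a randomised comparison with no true effect, a baseline covariate moves the arm estimate only through chance imbalance, so the criterion reacts to noise in the quantity under test. With a real effect, the odds ratio also moves because it is non-collapsible: adjusting for a prognostic covariate shifts it away from 1 even under perfect balance. Either way, movement of the estimate does not show that adjustment is needed.

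The criterion also cannot be applied without seeing the treatment effect. With an open list and no threshold, direction or order of steps, several final models fit the wording, and the ordinary Wald interval takes no account of the choice.

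Packing density is a separate problem. It is measured after randomisation and may lie on the path from coil type to recurrence. Conditioning on it can remove part of the effect of interest, or create an apparent effect where there is none. A rule that looks for movement in the arm estimate will tend to retain such a variable.

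**Working it through.** **1. The plan's own figure.** Inputs from section 9.1 and Table 5: recurrence 33.0% against 22.8%, two-sided 5%, 80% power, 1:1. With pooled variance and no continuity correction, the mean rate is 0.279.

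n per arm = [1.960 × √(2 × 0.279 × 0.721) + 0.8416 × √(0.33 × 0.67 + 0.228 × 0.772)]² / 0.102²
= (1.2432 + 0.5304)² / 0.010404 ≈ 302.3, so 303 per arm and 606 in total.

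Power at 300 per arm is 79.7%, and the odds ratio is (0.228/0.772)/(0.33/0.67) = 0.600. This reproduces N = 600 and the 0.60 end of the range in "the sample of 600 patients would provide 80% power to detect an odds ratio between 0.60 and 0.47"; the other end plays no part here. The sizing of the unadjusted test is therefore sound. The documents give no error rate for the selected model beyond the nominal 5%.

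**2. Selection among baseline covariates.** Simulated trials had no coil effect, N = 600, 1:1 allocation, about 33% recurrence and a two-sided 5% Wald test. Covariate strengths and cut-offs are assumptions, because the documents give none. The strong set has log-odds per SD of 0.3, 0.3, 0.7, 0.6 and 0.5. The ten-covariate set runs from 0 to 0.4. Site was not simulated. The table gives the percentage of trials declared significant.

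| Rule | 5 covariates, none prognostic | 5 moderate | 5 strong | 10 mixed |
|---|---|---|---|---|
| Unadjusted | 4.8 | 4.8 | 5.3 | 6.1 |
| Fixed set, no selection | 4.8 | 5.1 | 5.3 | 5.7 |
| Keep if p<0.05 or odds ratio changes >10% | 4.9 | 5.0 | 5.4 | 5.9 |
| Keep if the effect moves away from the null | 5.6 | 7.3 | 11.5 | 12.4 |
| Most significant model (all subsets in the first two columns, stepwise search in the last two) | 5.7 | 7.7 | 12.0 | 12.5 |
| Either the unadjusted or the mechanically selected result significant | 5.0 | 6.1 | 7.7 | 7.3 |
| Simulation standard error at 5% | 0.34 | 0.34 | 0.44 | 0.56 |

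The standard error is √(0.05 × 0.95/trials), with 4,000, 4,000, 2,500 and 1,500 trials. The 6.1% for the unadjusted test with ten covariates lies within two standard errors of 5%. Separate runs under similar assumptions gave 4.8% and 5.1% for the mechanical rule, 7.7% to 12.5% for the directed rule and 6.0% to 7.5% for either result.

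**3. Packing density.** Suppose packing = δ × arm + a × U + noise, and recurrence depends on U with coefficient γ but not on arm. Given arm and packing, the expected U is λ(packing − δ × arm). The arm term in the adjusted model then picks up roughly −γλδ although the coil does nothing. The bias needs both an arm difference (δ) and a shared cause (γ). If the shared cause raises packing and lowers recurrence, the bias runs against hydrogel.

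Simulated with 4,000 trials per setting and no coil effect, the adjusted test rejected as follows:

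- Arm difference 0.5 SD: 9.2% and 15.9% for the weaker and stronger assumed link with recurrence.
- Arm difference 1.0 SD: 18.7% and 41.3%.
- No link, or no arm difference: 4.2% to 5.5%.

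The unadjusted test stayed at about 5% throughout. Forcing packing density in or letting it be selected made almost no difference. Separate runs gave 16% to 43%.

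**4. Interactions.** For the seven named candidates tested at 5% each, if independent and with one term each, the chance of at least one false signal is 1 − 0.95⁷ = 30.2%.

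**The case against.** The plan states no direction. Read neutrally and applied mechanically to baseline covariates, the rule shows no detectable inflation in the table above. A reader might infer that the clause by itself inflates the false-positive rate. The documents do not support that: it takes a choice that favours a larger or more significant effect, which the plan permits but does not prescribe.

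A reader might also infer that the primary test is compromised. It is not. The chi-square test comes first, is the basis of Table 5 and involves no selection; the adjusted models are introduced as additional. Counting success on either odds ratio is likewise not a rule in the plan. Since both odds ratios will be reported, a wide gap between them would be visible.

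All of this stands, and it limits the point to the adjusted odds ratio. It does not remove the point. Powering both analyses without naming the deciding one leaves the adjusted result open to being read as confirmatory, and visibility of both estimates does not tell a reader whether the adjusted model was planned.

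On site, the section names it first among the candidates, and dropping it is only a possibility. No error figure is attached to that. Ignoring a stratification factor usually makes a test somewhat conservative, so the issue there is consistency with the design, not false positives.

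**Conclusion.** The point holds as a gap in control of the adjusted analysis. Section 9.2.1 allows the final model to be chosen with sight of, and partly because of, the treatment effect it will report, so the 5% error rate and the Wald interval of the adjusted odds ratio are not assured. Under no true effect the plausible range is about 5% (mechanical use), about 6% to 12% (covariates kept because they enlarge the effect) and about 5% to 8% (either odds ratio may count). These figures rest on assumed covariate strengths and cut-offs.

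Packing density is the larger hazard, at about 9% to 43% false positives. That range assumes an arm difference in packing together with a cause shared with recurrence. Fixing the covariate list would not cure it if packing density stayed on the list. The change should be made, but the unadjusted comparison is sound without it.

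**What to change.** - State which result carries the 5% test. The unadjusted chi-square test is the natural choice because Table 5 is sized on it; if the adjusted model is preferred, name that instead.
- Pre-specify one adjusted logistic model with arm, age, sex, aneurysm size, neck size, rupture status and a random intercept for site, with no selection. Section 9.2.2 already names these covariates for the packing-density model. With up to 50 sites, 600/50 = 12 subjects per site on average, which favours a random intercept over separate site terms.
- Delete the clause on change in the arm–outcome relationship.
- Leave packing density out of any model used to estimate the coil effect. Keep it as a secondary outcome.
- Label covariate-by-arm interactions exploratory.
- Apply the same model to the binary secondary outcomes.

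The cost is SAP wording only. No data or subjects are added, and the plan already names PROC GLIMMIX, which fits a random intercept. The downside is loss of freedom to trim the model.

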“HEAT”

New Generation **H**ydrogel **E**ndovascular **A**neurysm treatment **T**rial

September 4, 2014
Protocol #1908: Version 07

A randomized controlled trial of new generation Hydrogel
coils versus bare platinum coils in the endovascular
treatment of intracranial aneurysms

Sponsor: **Northwestern University**
[name].
[name]
[name]
[contact]
[contact]

Funder: **MicroVention, Inc.**
[name]
[name]

This protocol contains confidential information for use by the Investigators and their designated representatives participating in this clinical investigation. It should be held confidential and maintained in a secure location. By accepting this document, you agree to maintain the information as confidential and to use it only for the purpose of conducting the study.

1 Protocol Synopsis

FULL STUDY TITLE	New Generation Hydrogel Endovascular Aneurysm Treatment Trial
STUDY OBJECTIVES	Comparing initial complete occlusion, recanalization, retreatment and adverse event rates of the HydroCoil® Embolic System to those of bare platinum coils.
STUDY DESIGN	International, randomized, prospective, controlled, multicenter trial
DEVICES	Second generation hydrogel coils from the HydroCoil® Embolic System™ (including the HydroSoft®, HydroFill® and HydroFrame® and future FDA and HPB approved Hydrogel coils) (“Hydrogel Group”) and Platinum coils (“Platinum Group”)
TREATMENT POPULATION	Subjects with intracranial aneurysms between the ages of 18 and 75 years inclusive
ESTIMATED TRIAL SIZE	600 randomized subjects
NUMBER OF SITES	Approximately 50 sites inside and outside of the U.S.
PRIMARY ENDPOINT	Aneurysm recurrence at any point during follow-up defined as any progression on the Raymond aneurysm occlusion scale.
SECONDARY ENDPOINTS	
• Packing density as measured by volumetric filling of the aneurysm• Clinical outcome at 18 to 24 months (mRS)• Peri-procedural and post-procedural adverse events related to the procedure and/or the device.• Mortality rate• Initial complete occlusion• Aneurysm retreatment• Hemorrhage from target aneurysm during follow-up• Aneurysm occlusion stability• Major vs. minor recurrence
VISIT SCHEDULE	Baseline, Procedure, 1 day post-procedure, 3 days to 28 days, 3 months to 12 months, 18 months to 24 months
PRINCIPAL INVESTIGATOR OF THE STUDY	[name]. [name] [name] [contact] [contact]

**CORE
LABORATORY
("CORE LAB")**

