5.2 Study Duration and Enrollment

The duration of the open enrollment phase will be 24 months or until the required number of patients are enrolled. Each patient will have a post-procedure follow-up of at least 18 months.

The number of Subjects to be enrolled, and randomized, in the study is up to 600. This sample size calculated to provide sufficient statistical power to show the anticipated difference in initial occlusion and recurrence rates between the 2 study arms (see section 9 for detailed statistical analysis). Patients will be recruited from up to 50 national and international centers. Each Investigational Site will be expected to enroll at least 20 Subjects. Each site must meet the eligibility criteria.

A multidisciplinary approach is expected from each qualified study center. The Neurovascular teams should include the appropriate specialties for the proper conduct of the study e.g., neurointerventionalist(s), experienced in intracranial aneurysm coiling, neurosurgeon(s), and study coordinator(s). In addition, the treating physician must meet a minimal level of expertise consisting of at least 5 successful intracranial aneurysm coiling procedures utilizing the HydroCoil Embolic system prior to enrolling patients into the study.

Each site must provide written approval from their reviewing Institutional Review Board (IRB) and all other required regulatory documentation prior to consenting and enrolling the first Subject.

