6.13 Study Completion

Once a subject completes all study follow-up visits which include the 18 to 24 month visit, the Final Follow-Up eCRF must be completed. During the course of the study, it is possible that subjects will be

withdrawn from the study prior to completing the final 18 to 24 months visit. Factors leading to Subject withdrawal may include, but are not limited to the following:

- **Subject Withdrawal** - A Subject may voluntarily withdraw from the study at any time for any reason, whether disclosed or undisclosed, without affecting their future medical treatment or benefits. In addition, if a patient refuses follow-up examinations and evaluations the investigator may remove her/him from the study after appropriate notice.
- **Subject Lost to Follow-Up** – If the subject does not show up to the planned follow-up visits, attempts should be made to contact her/him. If after at least three (3) attempts the subject remains unreachable, she/he may be withdrawn from the study. The research team must document at least three contact attempts before declaring a subject as lost to follow-up.
- **Subject Death** - When a Subject dies, the ADVERSE EVENT and STUDY EXIT eCRFs must be completed immediately (within 24 hours of the event). If available, documents such as the death summary, the autopsy report and a copy of the death certificate shall be provided to the principal investigator of the site and the Sponsor, Northwestern University, and the funder, MicroVenton. Personal identifiers should be removed from any documentation provided. The site's IRB shall also be notified promptly.

If a subject was withdrawn for any of the above mentioned reasons, the Study Exit eCRF form must be completed.

7 Management of Adverse Events

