8.2 IRB Approval

The Investigator or the study coordinator is responsible for submitting the study protocol and any changes issued by the Sponsor during the course of the study for IRB approval prior to any Subject enrollment and amendments taking effect as well as obtain renewals at periods determined by the IRB for the duration of the study.

9 Statistical Methods

Primary analysis of primary and secondary outcomes will be based on the intent-to-treat (ITT) principle. Secondary analyses will examine differences based on per protocol principles, as well as a detailed analysis of missing data, should there be any (see below).

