The rates of initial complete occlusion, partial occlusion, recanalization, retreatment, or hemorrhage from the target aneurysm during follow-up (and other binary outcomes) will be analyzed similar to the primary endpoints. Packing density will be analyzed by comparing means or medians (depending on the underlying distribution) between groups. Additionally, this will be compared using linear regression models (PROC REG or PROC MIXED, as above) adjusting for potential confounders including site, age, gender, aneurysm and neck size, and rupture status. Clinical outcomes and quality of life will be compared between groups using models appropriate for repeated measures (generalized linear mixed models). This will take into account changes in these outcomes over time as well as the 18-month evaluation and can accommodate some missing data as it does not require only complete cases be used but rather uses an available data analysis. Again univariate and multivariate results (means and 95% Confidence intervals) will be presented.

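### Retreatment and target-aneurysm hemorrhage are planned as yes/no outcomes with an unsettled denominator, although follow-up is unequal and event dates can be had; a time-to-event analysis would remove the choice.

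*Combined protocol and SAP*

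**What the plan says.** Section 9.2.2 groups several secondary outcomes and says that "retreatment, or hemorrhage from the target aneurysm during follow-up (and other binary outcomes) will be analyzed similar to the primary endpoints". The method carried over from 9.2.1 is: "Chi-square tests (simple logistic regression) will be used to determine if rates of recurrence differ by coil type", followed by multiple logistic regression with odds ratios. The synopsis lists "Mortality rate" as a secondary endpoint. Section 9.2.2 does not name it, so it is covered only as one of the other binary outcomes. No Kaplan-Meier, log-rank, Cox, person-time or competing-risk method appears anywhere.

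On follow-up, section 5.2 says: "Each patient will have a post-procedure follow-up of at least 18 months". The final visit falls anywhere from 18 to 24 months (6.10), and section 6.13 expects that some subjects will be "withdrawn from the study prior to completing the final 18 to 24 months visit".

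On incomplete data, 9.2.1 says: "Patterns of missing data and dropout will be examined to determine if complete case analysis or available data analyses are appropriate". It adds: "If imputation methods are called for, PROC MI and PROC MIANALYSE will be used and results presented".

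On who is analysed, section 9 opens with: "Primary analysis of primary and secondary outcomes will be based on the intent-to-treat (ITT) principle". Section 6.1 removes subjects who choose to withdraw from the analysis, while section 5.3.1 allows use of what was collected before they withdrew.

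On dates, adverse-event reports carry the date and time of the event (7.2). A retreatment is entered as an unscheduled visit (6.11.1), so its date can be derived, although no retreatment-date field is described.

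**The concern.** A yes/no analysis needs a rule for the subject who leaves event-free at, say, month 5. Three rules fit a binary analysis: count the subject as no event, drop the subject unless an event came first, or drop everyone who left early. They give different answers when loss differs between arms, and the first two err in opposite directions. The plan does not say which applies, and it defers the missing-data route until the data pattern has been examined.

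Retreatment is where this matters most. Lower retreatment is part of the study hypothesis (4.1), and Table 5 gives the difference detectable with 600 subjects. The operator knows the coil type and no patient blinding is described, so differential loss cannot be excluded. The plan states no expected loss. Its own Table 2 shows 51% to 90% followed up in earlier hydrogel studies, so substantial loss is plausible, but those figures are not split by arm.

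**Working it through.** **Inputs from the documents.** 300 per arm, two-sided 5%, chi-square (9.1); retreatment 17.4% platinum and 9.6% hydrogel (Table 5). **Assumed:** all loss rates, and loss independent of the event.

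**1. Table 5 reproduced.** Pooled proportion (0.174 + 0.096)/2 = 0.135. Null SE = √(2 × 0.135 × 0.865/300) = 0.02790. Alternative SE = √((0.174 × 0.826 + 0.096 × 0.904)/300) = 0.02772. Power = Φ((0.078 − 1.96 × 0.02790)/0.02772) = Φ(0.841) = 80.0%. This figure leaves no room for loss: with 270 per arm (10% lost) complete-case power is 75.7%, and with 240 (20% lost) it is 70.7%.

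**2. Bias with no true difference, closed form.** Take 17.4% in both arms by 18 months, constant hazard, and loss uniform over 0-18 months. The cumulative hazard is −ln(1 − 0.174) = 0.1912. The share of lost subjects whose event is seen before they leave is 1 − 0.174/0.1912 = 0.090. With loss d:
- Lost counted as event-free: (1 − d) × 0.174 + d × 0.090.
- Only subjects with an event or complete follow-up: the same numerator over (1 − d) + d × 0.090.
- Strict complete case: 0.174 whatever d is.

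| Loss, arm A vs B | Lost = event-free | Event or complete | Strict complete case |
|---|---|---|---|
| 10% vs 10% | 16.6% vs 16.6% | 18.2% vs 18.2% | no difference |
| 10% vs 20% | 16.6% vs 15.7% | 18.2% vs 19.2% | no difference |
| 10% vs 30% | 16.6% vs 14.9% | 18.2% vs 20.5% | no difference |

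The spurious difference is 0.8 to 1.7 points under the first rule and 1.0 to 2.2 points the other way under the second. Table 5's detectable difference is 7.8 points. Under the first rule the false-positive rate is 5.9% and 8.8% in the two unequal rows.

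**3. False-positive rate by simulation.** Here loss comes earlier: uniform over months 1-12, final visit uniform over 18-24 months, 17.4% risk at 21 months in both arms. Ranges are across repeated runs.

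| Rule | 10% vs 20% | 10% vs 25% | 10% vs 30% |
|---|---|---|---|
| Lost = event-free | 6.4-6.6% | 8.8-10.3% | 12.5-13.2% |

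Keeping subjects with an event or complete follow-up gives 6.0-7.0% at the two larger imbalances. Strict complete case gives 5.0-5.2% there. Log-rank stays at 4.8-5.5%.

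**4. Power at 17.4% vs 9.6%, same simulation.**
- Equal 20% loss: log-rank 74%, strict complete case 71%.
- Platinum 25%, hydrogel 10%: log-rank 76%, strict complete case 72%, lost counted as event-free 56-57%.
- Imbalance reversed: lost counted as event-free about 88%, against 74% for log-rank. That excess is bias in hydrogel's favour.

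As a cross-check, the hazard ratio is ln(0.904)/ln(0.826) = 0.528. With 300 × (0.174 + 0.096) = 81 events and no loss, Schoenfeld's formula gives Φ(√81/2 × 0.639 − 1.96) = 82.0%, so N does not change.

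**5. Rare events.** At an assumed 2% risk (the scale of hemorrhage or death), counting the lost as event-free gives a false-positive rate of about 5.4% even at 10% vs 30% loss.

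**The case against.** A reader might infer that the plan fixes the denominator at all randomized subjects, so that unequal loss becomes a false difference. The documents do not say so. Section 9.2.1 names complete-case, available-data and imputation routes, and none of them counts lost subjects as event-free. The 9-13% error rate belongs to that one rule, and strict complete case shows no inflation. The imbalances behind it are also large: 15 to 20 points, with no support in the documents. A constant hazard overstates the effect if retreatment comes early. Section 3.5 cites a trial with 8.8% early and 9.0% late retreatment, split at 3 months. With that timing, 10% vs 25% loss gives 6.5% and 10% vs 30% gives 7.4%. Finally, log-rank needs censoring unrelated to prognosis, so it does not cure informative loss.

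All of that stands, and it limits the size of the point. It does not settle the denominator. An available-data mixed model recovers nothing when the outcome, ever retreated, is a single value per subject. Imputation could work if it used arm and time observed, but no model is given. Strict complete case discards known follow-up, and if it means attending the final visit it would remove the deaths themselves, since 6.13 lists death as a reason for early exit.

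**Conclusion.** The point holds in limited form. Outcomes that unfold over unequal follow-up are planned as binary, the rule for partial follow-up is left open, and sections 5.3.1, 6.1 and 9 conflict on withdrawn subjects. Both the size and the direction of any bias in the retreatment comparison then depend on a rule chosen after the data are seen. Under the assumed imbalances the error rate lies between 5% and about 13%, according to the rule and the amount of loss. Under equal loss there is no false difference. The more certain gain from log-rank is about 3-4 points of power over strict complete case, and Table 5's 80% for retreatment holds only with no loss.

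The documents do not support saying that the plan will produce a false difference, or that hemorrhage and mortality comparisons are materially biased. All the affected endpoints are secondary.

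**What to change.** In 9.2.2, take retreatment, target-aneurysm hemorrhage and mortality out of the sentence that refers back to the primary endpoint.
- **Retreatment:** time from randomization to first event in all randomized subjects, censored at last contact. Give the log-rank test, Cox hazard ratio, and cumulative incidence at 18 months with 95% CI, treating death as a competing event.
- **Hemorrhage:** the same approach.
- **Mortality:** named explicitly, with Kaplan-Meier estimates.
- **Crude proportions:** kept as description.

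Align 5.3.1 and 6.1 so that data collected before withdrawal are included; screen failures, who are never randomized, can stay excluded. Confirm that the unscheduled-visit form yields a retreatment date and that the last-contact date is captured. Report loss by arm with reasons, because censoring at last contact assumes loss independent of prognosis.

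The cost is protocol and SAP wording and a few lines of SAS. No patients or visits are added, and N stays at 600.
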